8.2 Primary endpoint

8.2.1 Patient characteristics at baseline

Analysis set	Analysis population
Details of analysis	Aggregate patient characteristics as indicated in the definition. Variables observed in quantitative values are calculated as summary statistics, and qualitative variables are tabulated in terms of the number of patients and proportions of patients relative to overall patients and evaluated patients.
Definition	
- Age- Sex- Body mass index (BMI)- Eastern Cooperative Oncology Group Performance Status (ECOG PS)- International Metastatic RCC Database Consortium (IMDC) risk score- Pathological diagnosis: Fuhrman grade, histological type, Sarcomatoid component- Tumor-node-metastasis (TNM) classification,- Number of metastatic organs and site of metastases- Complications- Nephrectomy- Renal function: estimated glomerular filtration rate (eGFR), proteinuria- C-reactive protein (CRP)- Smoking history- Concomitant drugs

8.2.2 Details of complications

Analysis set	Analysis population
--------------	---------------------

Details of analysis	Calculate the number and proportion of patients by SOC and PT for each complication.
---------------------	--

8.2.3 Details of concomitant drugs

Analysis set	Analysis population
Details of analysis	Tabulate the frequency of concomitant drug use by drug name.

8.3 Secondary endpoint

8.3.1 Efficacy endpoint

8.3.1.1 Time-to-treatment failure (TTF) of avelumab plus axitinib as first-line therapy

Analysis set	Analysis population
Details of analysis	
The Kaplan-Meier methods is used to plot the duration of TTF and calculate survival probability (estimate, 95% confidence interval), number of patients at risk, cumulative number of events, and cumulative number of censoring every 3 months.
 
In addition, the median duration of TTF, and incidence of events (/100 person-years) and the 95% confidence interval will be calculated.

Supplement	
<Calculation method for each 95% confidence interval>
 
Survival probability: Pointwise confidence limits
 
Median duration of TTF: Greenwood exponential formula
 
Incidence of events: Mantel-Haenszel method

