### **9.7.2. Analysis Methods**

Continuous variables will be summarized using descriptive statistics ie, number of non-missing values and number of missing values [ie, n (missing)], mean, median, standard deviation (SD), minimum, maximum and first and third quartile.

Qualitative variables will be summarized by frequency counts and percentages.

For the time-to-event endpoints, eg, TTF and Real-world PFS, the Kaplan-Meier estimates (product-limit estimates) will be presented together with a summary of associated statistics including the median Real-world PFS time with 2-sided 95% CIs. In particular, the Real-world PFS rate at several timepoints will be estimated with corresponding 2-sided 95% CIs. These endpoint will also be displayed graphically.

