##### **Other Secondary Endpoints**

See [Section 9.1.3](#). These endpoints will also be displayed graphically if necessary.

The SAP must be fixed before data lock. The final analysis will be performed after data lock and may modify the plans outlined in the protocol.

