5.2 Analysis population

Enrolled patients who meet all the inclusion criteria.

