8.3.1.2 Real-world PFS

Analysis set	Analysis population
Details of analysis	Perform the same analysis as in 8.3.1.1 for real-world PFS.

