8.3.1.4 TTF of avelumab

Analysis set	Analysis population
Details of analysis	Perform the same analysis as in 8.3.1.1 for TTF of avelumab.

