8.3.1.5 TTF of axitinib

Analysis set	Analysis population
Details of analysis	Perform the same analysis as in 8.3.1.1 for TTF of axitinib.

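### The SAP names the Mantel-Haenszel method for the confidence interval of a single-cohort event rate, where it gives no interval, and four time-to-event endpoints inherit the line

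*SAP*

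**What the plan says.** SAP 8.3.1.1 covers time to treatment failure of the combination. Besides the Kaplan-Meier output and the median, it states that "incidence of events (/100 person-years) and the 95% confidence interval will be calculated". The Supplement to that section lists a method for each 95% interval. The entry for this rate reads "Incidence of events: Mantel-Haenszel method".

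Three other sections take over the analysis unchanged:

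- SAP 8.3.1.2: "Perform the same analysis as in 8.3.1.1 for real-world PFS"
- SAP 8.3.1.4: "Perform the same analysis as in 8.3.1.1 for TTF of avelumab"
- SAP 8.3.1.5: "Perform the same analysis as in 8.3.1.1 for TTF of axitinib"

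All four analyses use the single population of SAP 5.2, defined as "Enrolled patients who meet all the inclusion criteria". SAP 7.3 fixes the level and sidedness of intervals (95%, two-sided) but no method.

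Protocol 9.7.2 says that for time-to-event endpoints "the Kaplan-Meier estimates (product-limit estimates) will be presented together with a summary of associated statistics", including the median and PFS rates at time points. It does not mention a person-time rate.

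**The concern.** The quantity to be reported is one crude rate: events divided by person-time in one cohort. Mantel-Haenszel is a method for pooling a comparison, either a rate ratio or a rate difference between two groups, over strata. It needs a second group, and it is useful only when there are strata to pool over. The study is a single-cohort chart review, and I found no comparator, stratification factor or set of weights for these endpoints in either document.

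If the line cannot be followed, the person programming the tables must pick an interval for four endpoints without guidance, possibly after seeing the data. Protocol section 12 foresees abstracts and publications. A methods statement copied from the SAP would then describe a calculation that was not done.

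**Working it through.** The documents give no event count, person-time or rate, so there is no planned figure to reproduce. The check has two parts.

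**1. Is the named method defined for the named quantity?**

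For person-time data with groups 1 and 0, where PT is the total person-time in a stratum:

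- Mantel-Haenszel rate ratio = Σ(D1 × PT0 / PT) / Σ(D0 × PT1 / PT)
- Its variance uses Σ(D × PT1 × PT0 / PT²), where D = D1 + D0
- The stratum weight for the rate difference is PT1 × PT0 / PT

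With one cohort there is no group 0, so D0 = 0 and PT0 = 0. Using the illustrative 31 events and 51.6 person-years derived below:

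- Rate ratio: (31 × 0 / 51.6) / (0 × 51.6 / 51.6) = 0/0, undefined
- Variance term: 31 × 51.6 × 0 / 51.6² = 0
- Rate-difference weight: 51.6 × 0 / 51.6 = 0

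No interval results. The point estimate, 100 × D / PT, is not affected.

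**2. What interval should a reader expect from a valid one-sample method?**

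Inputs from the documents:

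- About 70 patients, a number called flexible (Protocol 9.5, SAP 4)
- Index dates from 20 December 2019 to 20 December 2020, with observation to 20 June 2021 (Protocol 9.1), so about 6 to 18 months of follow-up
- Median PFS of 13.8 and 7.2 months for the two arms of the phase 3 trial cited in Protocol section 7

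Assumptions: uniform accrual over the 12 months, exponential event times, no other censoring, and a median of 24 months as the long end of the range.

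Formulas, with median m in months:

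- λ = ln 2 / m
- Event fraction p = 1 − [exp(−6λ) − exp(−18λ)] / (12λ)
- Expected events D = 70p, rounded to an integer for the intervals
- Person-years PY = 70p / λ / 12
- Exact Poisson limits: χ²(0.025; 2D) / (2 PY) and χ²(0.975; 2D + 2) / (2 PY)
- Log-rate limits: rate × exp(±1.96 / √D)

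For m = 13.8: λ = 0.05023, and p = 1 − (0.7398 − 0.4049) / 0.6027 = 0.444. Then D = 31.1 and PY = 31.1 / 0.05023 / 12 = 51.6. The rate is 100 × 31 / 51.6 = 60.1 per 100 person-years.

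| Assumed median (months) | Events | Person-years | Rate per 100 PY | Exact Poisson 95% CI | Log-rate 95% CI |
|---|---|---|---|---|---|
| 7.2 | 47 | 40.4 | 116.3 | 85.4 to 154.6 | 87.3 to 154.7 |
| 13.8 | 31 | 51.6 | 60.1 | 40.8 to 85.3 | 42.2 to 85.4 |
| 24 | 20 | 58.4 | 34.2 | 20.9 to 52.9 | 22.1 to 53.0 |

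The exact and log-rate limits differ by at most about 2 per 100 person-years (87.3 − 85.4 = 1.9). A plain normal interval, rate ± 1.96 × 100√D / PY, departs further. With 31 events it is 38.9 to 81.2, so its upper limit is about 4 below the exact one. With 47 events its upper limit is 149.5 against 154.6, about 5 below.

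**The case against.** The best defence is that the line is misnamed rather than unworkable. With a single stratum, a weighted rate collapses to the crude rate with a Poisson variance, and any competent analyst would produce that. The SAP does not state this reading, however, and it would still leave the scale open (normal, log or exact).

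It can also be said that the 0/0 result only restates in symbols that there is one group, for a ratio the SAP never requests. That is fair. The result shows why the method does not apply, and it measures nothing. The illustrative intervals do not size the defect either.

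The rate is an addition to secondary endpoints in a descriptive study. The protocol does not ask for it, and no conclusion turns on it. This stands and limits the weight of the point.

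Last, SAP section 1 refers to separately prepared sample tables and figures, which I have not seen. The supportable claim is that nothing in the protocol or SAP supplies a usable method. Unseen table layouts would not correct a wrong line in the SAP.

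**Conclusion.** The concern holds. The SAP assigns to a one-sample rate a method that needs a comparison, and four endpoints inherit it. The protocol offers no alternative, so the 95% interval for the event rate cannot be produced as written.

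The consequence is small: it affects only the width and reproducibility of the intervals around descriptive secondary rates. The primary endpoint (baseline characteristics), the point rates, the Kaplan-Meier estimates and the medians do not depend on the line. The conclusion about the method needs no assumption beyond the single-cohort design. The illustrative intervals rest on the accrual, exponential and censoring assumptions given above. They indicate that the exact and log-rate methods would agree closely, so either would serve.

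The Greenwood-based interval that the SAP names for the median is workable, and I do not count it as an error.

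**What to change.** Replace the line in the Supplement to SAP 8.3.1.1 with a named one-sample person-time interval, for example: *Incidence of events: exact Poisson (Garwood) interval*. A log-transformed rate interval is equally valid. State that it also applies to 8.3.1.2, 8.3.1.4 and 8.3.1.5. If a stratified or comparative rate was in fact intended, define the groups and strata instead.

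Make the change before the database is locked, since the protocol's analysis section says "The SAP must be fixed before data lock".

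The cost is one line of text and a short standard calculation, with no new data. Two small trade-offs should be accepted: exact Poisson limits are slightly conservative, and any interval of this kind assumes a roughly constant event rate over follow-up.

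Optionally, and only for clarity, a second line could state that the survival-probability limits are pointwise log-log limits and that the median interval comes from inverting them at a survival probability of 0.5. The correction does not depend on this.

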8.3.1.2 Real-world PFS

Analysis set	Analysis population
Details of analysis	Perform the same analysis as in 8.3.1.1 for real-world PFS.

8.3.1.3 Objective Response: OR

Analysis set	Analysis population
Details of analysis	
Tabulate the best overall response by presence of confirmed BOR, あ all patients, and evaluation method (RECIST and non-RECIST).
 
In addition, calculate the number and proportion of patients with ORR and its 95% confidence interval.

Supplement	<Calculation method for each 95% confidence interval>

ORR:Clopper-Pearson confidence interval

8.3.1.4 TTF of avelumab

Analysis set	Analysis population
Details of analysis	Perform the same analysis as in 8.3.1.1 for TTF of avelumab.

8.3.1.5 TTF of axitinib

Analysis set	Analysis population
Details of analysis	Perform the same analysis as in 8.3.1.1 for TTF of axitinib.

8.3.2 Continuation of first-line treatment

Analysis set	Analysis population
Details of analysis	Tabulate the duration of treatment (months), DI, dosing status, and reason for interruption, dose change, or discontinuation of avelumab and axitinib.
Definition	
• Avelumab DI= (actual dose)/(duration of avelumab treatment [weeks]/2) (mg/kg/2-week cycle)• Axitinib DI=(actual dose)/(duration of axitinib treatment [weeks])

8.3.3 Corticosteroid-related endpoints

8.3.3.1 Corticosteroid treatment for irAEs during avelumab plus axitinib treatment

Analysis set	Analysis population
Details of analysis	Tabulate the number of patients treated for irAE with corticosteroids. Presence of high-dose corticosteroids treatment (prednisolone equivalent of 40 mg or more) will also be tabulated.

8.3.3.2 Cumulative corticosteroids dosages for irAEs during avelumab plus axitinib treatment or monotherapy

Analysis set	Analysis population
Details of analysis	Calculate summary statistics of corticosteroids dosing information for irAE. The dosages to be tabulated are prednisolone equivalents.

	Presence of high-dose corticosteroids treatment (prednisolone equivalent of 40 mg or more) will also be tabulated.
Supplement	If the same patient received multiple doses of corticosteroids, each dose should be tabulated separately (including patients who received multiple doses of the same corticosteroid).

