### **9.1.2. Secondary endpoints**

- Efficacy endpoint
  - Time to treatment failure (TTF) of avelumab plus axitinib as a first-line therapy
  - Real-world PFS
  - Objective response (OR)
- Avelumab-related endpoints
  - TTF
  - Discontinuation and interruption of avelumab
  - Reason for discontinuation and interruption
- Axitinib-related endpoints
  - TTF
  - Dose increase, dose reduction, discontinuation, and interruption of axitinib
  - Reason for dose increase, dose reduction, discontinuation, and interruption
- Corticosteroid-related endpoints
  - Cumulative dose of corticosteroid for irAE during avelumab plus axitinib treatment
  - Duration of corticosteroid treatment for irAE during avelumab plus axitinib treatment
  - Number of corticosteroid administrations for irAE during avelumab plus axitinib treatment
- Infusion-related reaction-related endpoints

- Presence of pre-medication for potential infusion-related reaction of avelumab
- Drugs of pre-medication for infusion-related reaction of avelumab
- Presence of treatment for infusion-related reaction of avelumab
- Subsequent treatment-related endpoints
  - Drugs used after avelumab plus axitinib

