8.3.3.3 Duration of corticosteroids treatment for irAE during avelumab plus axitinib treatment

Analysis set	Analysis population
Details of analysis	Perform the same analysis as in 8.3.3.2 for duration of corticosteroid treatment.
Supplement	If the patient is on continuous corticosteroid treatment, the period should be up to the cut-off date (20 June, 2021).

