8.3.3.4 Number of corticosteroid administrations for irAEs during avelumab plus axitinib treatment

Analysis set	Analysis population
Details of analysis	Perform the same analysis as in 8.3.3.2 for the number of corticosteroid administrations.
Definition	Number of doses: the number of times treatment has been given, counting "treatment start to treatment end" as one dose.

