9 CHANGES FROM THE PROTOCOL

Not applicable.

Last page

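### The cumulative corticosteroid dose table includes monotherapy, while the patient-count, duration and number tables and the protocol are limited to combination treatment

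*SAP*

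**What the plan says.** Protocol 8.2 (objective 2) limits the description of corticosteroid use for irAEs to the period of combination therapy. Protocol 9.1.2 sets three corticosteroid endpoints, all with that limit; the first is "Cumulative dose of corticosteroid for irAE during avelumab plus axitinib treatment". Protocol 9.3.7 collects the corticosteroid data for the same period.

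The SAP has four corticosteroid tables. Three keep the protocol's window in their headings:
- 8.3.3.1: "Corticosteroid treatment for irAEs during avelumab plus axitinib treatment"
- 8.3.3.3: "Duration of corticosteroids treatment for irAE during avelumab plus axitinib treatment"
- 8.3.3.4: "Number of corticosteroid administrations for irAEs during avelumab plus axitinib treatment"

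The fourth, 8.3.3.2, is headed "Cumulative corticosteroids dosages for irAEs during avelumab plus axitinib treatment or monotherapy". SAP section 9, on changes from the protocol, reads "Not applicable".

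Both 8.3.3.1 and 8.3.3.2 also carry this sentence: "Presence of high-dose corticosteroids treatment (prednisolone equivalent of 40 mg or more) will also be tabulated". Neither gives a time unit.

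**The concern.** The four tables will be read together: how many patients had corticosteroids for irAEs, how much, for how long and how many times. That works only if all four draw on the same courses. As headed, they do not. A course given while the patient is on one drug alone adds to the dose table and is absent from the other three.

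The dose table also departs from the protocol endpoint, and the SAP does not say so. A programmer cannot tell whether the extra words in 8.3.3.2 are a deliberate widening or a slip. The SAP does not define monotherapy, and the word occurs in it only in that heading.

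Corticosteroid use is one of four secondary objectives, and the results are meant for abstracts and publications (protocol section 12).

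**Working it through.** The documents state no corticosteroid figure to reproduce. The check is a comparison of texts, followed by illustrations on assumed values.

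**1. Windows side by side**

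| Place | Content | Window |
|---|---|---|
| Protocol 8.2, objective 2 | corticosteroid use | combination |
| Protocol 9.1.2 | dose, duration, number | combination |
| Protocol 9.3.7 | data collected | combination |
| SAP 8.3.3.1 | patients treated | combination |
| SAP 8.3.3.2 | cumulative dose | combination or monotherapy |
| SAP 8.3.3.3 | duration | combination |
| SAP 8.3.3.4 | number | combination |
| SAP 9 | changes from protocol | none declared |

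**2. Possible readings.** SAP 8.3.3.3 and 8.3.3.4 each refer back to 8.3.3.2 for their analysis, so three readings are open.
- The headings govern. The dose table is wide and the other three are narrow.
- The back-reference carries the window. Dose, duration and number are wide, but 8.3.3.1 has no back-reference and stays narrow. All three endpoints then depart from the protocol.
- The extra words are a slip. All tables are narrow and the heading of 8.3.3.2 is wrong.

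The first two leave the four tables inconsistent and a protocol departure undeclared. The third leaves a wrong heading. Every reading requires a change to the SAP text.

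**3. Effect on one patient (assumed values).** Suppose one course of 10 mg/day for 14 days in the combination phase, then a separate course of 20 mg/day for 28 days that starts in a monotherapy phase.
- Course 1: 10 × 14 = 140 mg. Course 2: 20 × 28 = 560 mg. Sum: 700 mg over 14 + 28 = 42 days.

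| Window | Dose | Duration | Courses | Dose ÷ duration |
|---|---|---|---|---|
| As headed | 700 mg | 14 days | 1 | 700/14 = 50 mg/day |
| Combination throughout | 140 mg | 14 days | 1 | 140/14 = 10 mg/day |
| Wider window throughout | 700 mg | 42 days | 2 | 700/42 = 16.7 mg/day |

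The SAP plans no such ratio; it is shown only as what a reader would derive. SAP 8.3.3.2 lists multiple doses in one patient separately. If a dose there is a whole course, as 8.3.3.4 defines it, the dose table would hold two entries (140 and 560 mg) against one duration entry (14 days).

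**4. Effect on the patient count.** About 70 patients are expected (protocol 9.5). If *k* patients had corticosteroids for an irAE only in a monotherapy phase, the proportion in 8.3.3.1 changes by *k*/70 according to the window. The documents do not give *k*. For assumed values of 1, 3 and 5, the change is 1.4, 4.3 and 7.1 percentage points; for *k* = 0 it is nil.

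**5. The 40 mg cut-off.** The conversion table in SAP 6.3 is consistent with 5 mg divided by the equivalent amount (for example 5/0.75 = 6.67, shown as 6.7; 5/0.6 = 8.33, shown as 8.3), but it has no time unit either. The unit matters. A 28-day course at 20 mg/day (assumed) totals 560 mg, so it is high-dose if the cut-off applies to the course total and not high-dose if it applies per day, since 20 < 40.

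**The case against.** The strongest reply is that the mismatch rests on headings. The operative text of 8.3.3.3 and 8.3.3.4 sends the programmer back to 8.3.3.2, which could carry the wider window to duration and number. That is a fair reading, but it does not clear the problem: 8.3.3.1 would still cover fewer courses than the other three, and the protocol departure would be larger and still undeclared.

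Other points stand in full. The endpoints are descriptive, and only patients given corticosteroids for irAEs contribute. The tables differ only where there was corticosteroid use in a monotherapy phase, which the documents do not count. Protocol 9.7 lets the SAP modify the plan and asks for an amendment only for major changes to primary endpoints, so the procedural gap is a missing entry in SAP section 9. The table layouts are in a separate document (SAP section 1), which may settle some of this.

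Two stronger readings are tempting, and the documents support neither.
- A reader might infer that a course still running when one drug stops is cut off there for duration but not for dose, which would inflate any apparent daily dose. Nothing in the SAP truncates a course at that point. SAP 8.3.3.3 runs continuing treatment to the 20 June 2021 cut-off, and 8.3.3.4 counts each course from start to end. Both point to whole courses.
- A reader might infer that the 40 mg cut-off is a total dose, because it stands in the cumulative-dose section, and so would flag almost every treated patient. The same sentence stands first in 8.3.3.1, which has no cumulative dose, and the documents give no doses from which to project a proportion flagged. What is missing is the time unit, which an analyst would probably fill sensibly.

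**Conclusion.** The window conflict is a stated inconsistency, not merely missing detail. SAP 8.3.3.2 differs from the three neighbouring tables and from protocol 8.2, 9.1.2 and 9.3.7, while SAP section 9 declares no change. Followed as headed, the dose table covers a different set of courses from the other three.

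The impact is limited. It depends on how many courses were given in a monotherapy phase, which is unknown, and it is nil if there were none. Where a mismatch arises, the clearest case is a course that starts in a monotherapy phase; for courses that straddle the boundary, the SAP does not state the selection rule. The 40 mg point is secondary: a clarification of the unit, not evidence that the flag is meaningless.

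**What to change.** 1. Use one window in SAP 8.3.3.1 to 8.3.3.4 and define its start and end by date. The protocol's combination-treatment window is the default, which means removing the reference to monotherapy from the heading of 8.3.3.2.
2. State one course-selection rule for all four tables, for example whole courses that start within the window. Treat courses still running at 20 June 2021 the same way for dose as for duration.
3. If the wider window is wanted, apply it to all four tables and list the departure in SAP section 9. First confirm that corticosteroid data from monotherapy phases are collected, because protocol 9.3.7 covers only treatment with avelumab plus axitinib.
4. State whether the 40 mg prednisolone-equivalent cut-off is per day, per course or cumulative, and use it the same way wherever it is tabulated.

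With the default window, the cost is SAP wording and table layouts, to be settled before data lock. The wider window could require additional data collection if monotherapy-phase records were not captured.

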6.3 Derivation variables

1) Survival time analysis

It is defined as follows:

Endpoint	Start date	End date (event)	End date (censor)
Real-world PFS	Date treatment with avelumab and/or axitinib was initiated (if not on the same day, whichever occurs earlier)	Date of first disease progression (clinical evaluation based on radiological, laboratory, pathological, or other evaluation by the principal investigator) or death from any cause, whichever occurs earlier	Date of last confirmation of progression-free survival or start of subsequent treatment (whichever occurs earlier)
TTF of avelumab and axitinib	Date treatment with avelumab and/or axitinib was initiated	Date of completion of treatment with avelumab and/or axitinib	Date of last confirmation of progression-free survival or date of last dose in case of efficacy stopping (whichever date occurs earlier)
TTF of avelumab	Date treatment with avelumab was initiated	Date of completion of treatment with avelumab	Date of last confirmation of progression-free survival or date of last dose in case of efficacy stopping (whichever date occurs earlier)
TTF of axitinib	Date treatment with axitinib was initiated	Date of completion of treatment with axitinib	Date of last confirmation of progression-free survival or date of last dose in case of efficacy stopping (whichever date occurs earlier)

2) Objective response rate

ORR is defined as the proportion of patients with a CR or PR as the best overall response in tumor assessment during the observation period, as assessed by an investigator under actual clinical practice, including assessment based on RECIST ver. 1.1.

3) Calculation of duration

Duration	Definition
Duration of avelumab treatment	Date of last dose – date of initial dose + 14
Duration of axitinib treatment	Date of last dose – date of initial dose + 1
Duration of non-administration	Date of end – Date of start + 1

4) Corticosteroid equivalent dose (prednisolone equivalent)

This will be calculated as shown in the table below.

Generic name	Corresponding amount (mg)	Prednisolone conversion ratio
Cortisone	25	0.2
Hydrocortisone	20	0.25
Prednisolone	5	1
Methylprednisolone	4	1.25
Triamcinolone	4	1.25
Dexamethasone	0.75	6.7
Betamethasone	0.6	8.3

5) Date of initial dose

If avelumab and axitinib are administered for different durations, the earlier of the two dates should be used as the date of the initial dose.

6) Date of last confirmation of progression-free survival

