7.2 Summary statistics

Summary statistics for continuous variables will be calculated for observed and missing values, mean, median, standard deviation, minimum, maximum, first quartile, third quartile, etc.

Summary statistics for categorical variables will be calculated for frequency and proportion.

Other statistics, if calculated, will be described separately.

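### The cumulative corticosteroid table in SAP 8.3.3.2 lists each dose of a patient separately, and nothing in the SAP sums dose within a patient

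*SAP*

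**What the plan says.** Protocol 9.1.2 lists three corticosteroid endpoints for irAE, all during combination treatment: cumulative dose, duration, and number of administrations. Protocol 9.3.7 collects dose and cumulative dose as separate items. They serve secondary objective 2 (protocol 8.2), which is to describe corticosteroid use for irAE.

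The SAP handles them as follows.

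- **8.3.3.1** works at patient level: "Tabulate the number of patients treated for irAE with corticosteroids".
- **8.3.3.2** has the heading "Cumulative corticosteroids dosages for irAEs during avelumab plus axitinib treatment or monotherapy". It asks for summary statistics of dosing information in prednisolone equivalents, and adds: "Presence of high-dose corticosteroids treatment (prednisolone equivalent of 40 mg or more) will also be tabulated". Its Supplement then states: "If the same patient received multiple doses of corticosteroids, each dose should be tabulated separately". The rule expressly includes repeat use of the same drug.
- **8.3.3.3** reads: "Perform the same analysis as in 8.3.3.2 for duration of corticosteroid treatment". Its own Supplement adds only that ongoing treatment runs to 20 June 2021.
- **8.3.3.4** uses the same cross-reference for the number of administrations, and defines one dose as one course from start to end of treatment.
- **6.3** gives prednisolone conversion ratios in item 4, with no rule for summing. Item 3 defines three durations, for avelumab, axitinib and "Duration of non-administration". None is for corticosteroid.
- **7.2** sets the statistics for continuous variables: "mean, median, standard deviation, minimum, maximum, first quartile, third quartile".
- **Section 9** declares no change from the protocol.

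**The concern.** A cumulative dose is a sum, yet the Supplement to 8.3.3.2 keeps the parts of that sum apart and no other section puts them together. A programmer who follows the text will produce a table labelled cumulative whose n, SD and quartiles belong to rows. A patient with three courses contributes three smaller values instead of one large one.

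Description is the whole purpose of this study, so the unit described matters. Readers of a table with that label will take it as exposure per patient. For duration, and for the count in 8.3.3.4, they cannot tell whether the cross-reference brings the row rule with it or only the summary statistics.

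**Working it through.** **1. Is a within-patient sum defined anywhere?** The SAP sections on corticosteroids are 6.3 and 8.3.3.1 to 8.3.3.4. None contains one. The ratios in 6.3 are not the problem: each equals 5 mg divided by the listed amount (dexamethasone 5/0.75 = 6.67, shown as 6.7; betamethasone 5/0.6 = 8.33, shown as 8.3).

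**2. What is a row?** 8.3.3.2 does not define *dose*. By the definition in 8.3.3.4 a row is a course. The 40 mg threshold fits a dose level better than a course total. On either reading, a row is not the patient's total once that patient has more than one row.

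**3. Effect on the mean, if a row is a course total.** Let T be total dose, C courses and N treated patients. The row mean is T/C and the patient mean is T/N, so

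row mean / patient mean = (T/C)/(T/N) = N/C.

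| Courses per patient (C/N) | Row mean lower by 1 − N/C |
|---|---|
| 1.0 | 0% |
| 1.05 | 5% |
| 1.1 | 9% |
| 1.2 | 17% |
| 1.5 | 33% |

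The same factor holds for days if courses do not overlap. If a row is a dose level with its own total, the factor is N/R with R rows and R ≥ C, so the gap is at least as large. If a row is mg/day, the table is not a cumulative amount at all.

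**4. Effect on the other statistics: two invented examples (mg).**

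A: one patient with 600 + 200 + 100, and three with 400, 300 and 500. B: one patient with 1000 + 1000, and three with 100, 200 and 300.

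| | n | Mean | Median | SD | Max |
|---|---|---|---|---|---|
| A, rows | 6 | 350 | 350 | 187 | 600 |
| A, patients | 4 | 525 | 450 | 263 | 900 |
| B, rows | 5 | 520 | 300 | 444 | 1000 |
| B, patients | 4 | 650 | 250 | 904 | 2000 |

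Means: 350/525 = 4/6 and 520/650 = 4/5, as the formula requires. Medians: 350/450 is 22% lower, and 300/250 is 20% higher. The median error therefore has no fixed direction.

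**5. Simulated median gap.** The inputs are assumptions, because the documents give no number treated, repeat rate or dose distribution: 20 treated patients; a second course with probability p; log-normal course dose with median 400 mg, multiplied by k in patients with two courses; 3,000 replicates per setting. Row median against patient median (mg) at log-SD 1:

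| p | k = 0.5 | k = 1 | k = 2 | k = 4 |
|---|---|---|---|---|
| 0.1 | 371 vs 428 (−13%) | 415 vs 462 (−10%) | 464 vs 477 (−3%) | 518 vs 487 (+6%) |
| 0.2 | 336 vs 440 (−24%) | 408 vs 508 (−20%) | 523 vs 580 (−10%) | 644 vs 603 (+7%) |
| 0.5 | 261 vs 461 (−43%) | 412 vs 691 (−40%) | 651 vs 1032 (−37%) | 1075 vs 1625 (−34%) |

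Over log-SD 0.5, 1 and 1.5 and all four k, the gap runs from −16% to +8% at p = 0.1, −28% to +21% at p = 0.2, and −49% to −25% at p = 0.5. Repeat runs agreed to within about 1 percentage point. At p = 0.2 and log-SD 1, the gaps for k = 0.5, 1, 2 and 4 were −23, −20, −12 and 0% with 10 treated patients, and −24, −19, −8 and +9% with 30.

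**6. What can be recovered?** 8.3.3.1 gives the number of patients treated. If rows are course totals and the windows match, patient mean = rows × row mean / patients treated (A: 6 × 350/4 = 525). The per-patient median, quartiles, SD and range cannot be rebuilt.

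**7. The cross-references.** If the row rule carries over to 8.3.3.4, every count is 1, which is pointless. That suggests the cross-reference may bring only the summary statistics. On the other hand, SAP 8.3.1.2, 8.3.1.4 and 8.3.1.5 refer back to 8.3.1.1 in the same way, and there the Supplement on confidence intervals presumably does carry over. The text supports both readings.

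**The case against.** The best defence is that the row is a course, as 8.3.3.4 defines it, and that *cumulative* means the total within a course. Protocol 9.3.7 collects cumulative dose, so a derivation rule may be unnecessary. The protocol never says per patient, and protocol 9.7 lets the SAP modify its plans. On that reading section 9 omits nothing, and what remains is an undefined term. This is a coherent intention, but 8.3.3.2 does not state it, the 40 mg threshold sits badly with it, and it still yields no patient total.

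SAP section 1 says results will be presented in a separate set of sample tables and figures, which could fix the row unit and labels. That document presents the SAP's analyses, so it cannot be assumed to overturn an explicit rule in the SAP.

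Three limits stand. The carry-over to duration is an inference. The percentages rest on assumed inputs; the extremes need half the treated patients to have a second course, or repeaters to receive four times the dose per course. The endpoint is secondary and descriptive, and a by-course description still informs objective 2.

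**Conclusion.** The concern holds and should be fixed. SAP 8.3.3.2 is labelled cumulative, orders separate tabulation of each dose, and has no within-patient sum behind it, while section 9 tells the reader that the protocol endpoint is unchanged.

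If rows are course totals, the mean is understated by exactly 1 − N/C. The maximum cannot exceed the per-patient maximum, and the median may err in either direction. If no patient has a repeat course (one row per patient), the effect is zero. The real size cannot be stated from the documents. Confidence is high for dose and lower for duration, where the rule is only implied.

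**What to change.** - In 8.3.3.2 and 8.3.3.3, derive one record per treated patient: total prednisolone-equivalent dose and total days over all irAE courses, with overlapping days counted once. Summarise over treated patients and state n.
- Keep the by-course table as a supplement labelled as courses, and define *dose* there.
- If a within-course total was intended, say so in the heading of 8.3.3.2 and record it in SAP section 9.
- In 8.3.3.4, state that the count is courses per patient and that the Supplement to 8.3.3.2 does not apply.
- Use one analysis window for all three endpoints. At present only the 8.3.3.2 heading adds monotherapy, and only 8.3.3.3 sets an end date for ongoing treatment.

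The cost is SAP wording and one aggregation step. Protocol 9.3.7 already collects dates, drug, dose, cumulative dose, duration and number of administrations.
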